12.3 Appendix 3: Instructions for Subjects Moving from Protocol v1.0 to Protocol v2.0

Visit Schedule

Subjects who have entered the study under protocol v1.0, upon signing the updated informed consent, adapted their visit frequency according to [Table 1](#) Schedule of Assessments. For example, if the subject signs the informed consent for protocol v2.0 at scheduled week 3 (according to protocol v1.0), subject will attend clinic at week 4, week 6 and all subsequent visits as per Schedule of Assessments.

Dosing Instructions for Subjects Moving from Protocol v1.0 to Protocol v2.0 Dosing

Study drug will be dosed TIW throughout the Treatment Period, unless otherwise specified.

Subjects who have entered the study under protocol version 1.0 should, upon signing the updated informed consent, adapt their dose frequency and dose amount. At this visit it is first determined if the subject would need a dose titration according to the dose adjustment rules as per Section [5.1.2](#). Once that is established, patients are converted per the below instructions. The dose assigned must not exceed the maximum allowed dose of 3.0 mg/kg bodyweight or 300 mg per administration, whichever is lower. For subjects on permanent dialysis dose assigned must not exceed 3.0 mg/kg (based on dry weight in HD subjects and weight minus abdominal fluid based on last filling in peritoneal dialysis subjects) or 400 mg per administration, whichever is lower.

- a) Subjects in the correction period or maintenance period on TIW dosing, will continue on TIW dosing for the remainder of the treatment period. If needed their dose will be adjusted according to the conversion table below, at the visit when the updated informed consent is signed.

Current TIW dose (mg)	20	40	50	70	100	120	150	200	250	300	350	400
If no dose titration needed	20	40	50	70	100	100	150	200	250	300	300	300
If up titration needed*	40	50	70	100	150	150	200	250	300	300	300	300
If down titration needed*	#	20	40	50	70	100	100	150	200	250	300	300

- b) Subjects in the maintenance period on BIW dosing will change to TIW dosing immediately, per the conversion table below, at the visit when the updated informed consent is signed.

Current BIW maintenance dose (mg)	20	40	50	70	100	120	150	200	250	300	350	400
If no dose titration needed	20	20	40	50	70	70	100	150	150	200	250	250
If up titration needed*	20	40	40	70	70	100	150	150	200	250	250	300
If down titration needed*	#	20	20	40	50	70	70	100	150	150	200	200

- c) Subjects in the maintenance period on QW dosing will change to TIW dosing immediately, per the conversion table below, at the visit when the updated informed consent is signed.

Current QW maintenance dose (mg)	20	40	50	70	100	120	150	200	250	300	350	400
If no dose titration needed	20	20	20	20	40	40	50	70	70	100	100	150
If up titration needed*	20	20	20	40	40	50	70	70	100	100	150	150
If down titration needed*	#	#	20	20	20	40	40	50	70	70	100	100

* Up or down titrations were only applicable when the criteria for dose adjustment has been met

Contact the medical monitor if down titration is needed

Note: There are no adaptations to dose frequency or dose amount for subjects moving from Protocol v2.0 to Protocol v2.1.

ESA Rescue Therapy

Protocol v2.0 allows subjects to receive ESA rescue treatment twice. If a third ESA treatment is required the subject will be discontinued from the study treatment.

If, upon implementation of protocol v2.0, a subject has already received 3 or more ESA treatments (under protocol v1.0) they can initially continue in the study. The subject will however, be discontinued from study treatment if a further ESA rescue treatment is required.

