5.1.2 Changes in Study Drug Dose

Dose adjustments are permitted from week 4 onward, and every 4 weeks thereafter. All dose adjustments are made to maintain study subjects' Hb level within the predefined target range and are based on Hb values using the HemoCue® device, a point-of-care device.

Dose adjustments will follow unique dose adjustment rules [Table 3](#).

Table 3 Dose Adjustment Rules

Change in Hb over past 4 weeks (g/dL) ^a	Correction Period	Maintenance Period		
	(When Hb correction has not been reached)	Hb <10.5 g/dL	Hb 10.5 to <12.0 g/dL	Hb 12.0 to <13.0 g/dL
< -1.0	↑	↑	↑	No change
-1.0 to 1.0	↑	↑	No change	↓
> 1.0	No change	No change	↓	↓

^a Subtract 4 weeks' previous Hb value from the present Hb value to calculate the change.

- All dose adjustments are made based on Hb values using HemoCue, a point-of-care device.
- If the dose adjustment is 'No change' per [Table 3](#), the next dose adjustment review is 4 weeks after that visit.
- Dose increases by 1 dose step (↑) and reductions by 1 dose step (↓) are pre-set per the dose steps.
- The dose steps are as follows: 20, 40, 50, 70, 100, 150, 200, 250 and 300 mg.
- The maximum dose is the dose step corresponding to 3.0 mg/kg per administration or 300 mg, whichever is lower. The default weight is initially set as weight measured at day 1. At study visits where weight is collected, the maximum allowed dose step and the default weight for a subject will be adjusted if the weight change is ≥ 5% compared to the previous default weight collected in the study. For randomized subjects who require chronic dialysis during the treatment period, the maximum dose step is the dose step corresponding to 3.0 mg/kg per administration or 400 mg, whichever is lower.
- At week 4 only, in a subject whose BL Hb level was < 8.0 g/dL, if the dose adjustment is to increase, then dose increase could be made with either a 1 or 2 step increase per investigator's discretion to minimize the probability of requiring rescue therapy treatment.

- Contact the Medical Monitor if dose adjustments would lead to doses outside the limits of the dose step range; i.e., lower than 20 mg or higher than 300 mg.
- If there is a safety concern, investigators may deviate from the dose adjustment rules. This should be discussed with the Medical Monitor and documented in the source documentation.

At Any Time when Hb \geq 13.0 g/dL

- Stop dosing
- Resume dosing when Hb < 12.0 g/dL at a dose that is reduced by 2 steps

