- Next dose adjustment review is 4 weeks after dose resumption and in 4-weekly intervals thereafter.

Dose Adjustment for Excessive Hematopoiesis

At any time during the Treatment Period:

- If Hb increases by > 2.0 g/dL within 4 weeks, the dose should be reduced by 1 dose step.

Note: Only 1 dose reduction for excessive hematopoiesis is recommended within a period of 4 weeks. If a blood transfusion or ESA rescue treatment has been performed within 2 weeks of meeting the criteria for excessive hematopoiesis, it is recommended not to perform a dose reduction for excessive hematopoiesis.

After a dose adjustment due to excessive hematopoiesis, the subject's next dose adjustment review will occur 4 weeks later, and in 4-weekly intervals thereafter. If the dose adjustment interval falls on a non-visit study week, the dose adjustment review should be performed at the next scheduled clinic visit.

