Appendix 3: Protocol Instructions Subjects Moving from Protocol v1.0 to Protocol v2.0

Visit Schedule

Subjects who have entered the study under protocol v1.0 should, upon signing the updated informed consent, adapt their visit frequency according to Table 1, Schedule of Assessments.

Dosing Instructions for Subjects Moving from Protocol v1.0 to Protocol v2.0

Study drug will be dosed TIW throughout the Treatment Period, unless otherwise specified.

Subjects who have entered the study under protocol version 1.0 should, upon signing the updated informed consent, adapt their dose frequency and dose amount. At this visit it is first determined if the subject would need a dose titration according to the dose adjustment rules. Once that is established, patients are converted per the below instructions. The dose assigned must not exceed the maximum allowed dose of 3.0 mg/kg bodyweight or 300 mg per administration, whichever is lower. For subjects on permanent dialysis, the dose assigned must not exceed 3.0 mg/kg (based on dry weight in HD subjects and weight minus abdominal fluid based on last filling in peritoneal dialysis subjects) or 400 mg per administration, whichever is lower.

Subjects in the correction period or maintenance period on TIW dosing will continue on TIW dosing for the remainder of the treatment period. If needed, their dose will be adjusted according to the conversion table below, at the visit when the updated informed consent is signed.

Current TIW dose (mg)	20	40	50	70	100	120	150	200	250	300	350	400
If no dose titration needed	20	40	50	70	100	100	150	200	250	300	300	300
If up titration needed*	40	50	70	100	150	150	200	250	300	300	300	300
If down titration needed*	#	20	40	50	70	100	100	150	200	250	300	300

- a) Subjects in the maintenance period on BIW dosing will change to TIW dosing immediately, per conversion table below, at the visit when the updated informed consent is signed.

Current BIW maintenance dose (mg)	20	40	50	70	100	120	150	200	250	300	350	400
If no dose titration needed	20	20	40	50	70	70	100	150	150	200	250	250
If up titration needed*	20	40	40	70	70	100	150	150	200	250	250	300
If down titration needed*	#	20	20	40	50	70	70	100	150	150	200	200

- b) Subjects in the maintenance period on QW dosing will change to TIW dosing immediately, per conversion table below, at the visit when the updated informed consent is signed.

Current QW maintenance dose (mg)	20	40	50	70	100	120	150	200	250	300	350	400

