If no dose titration needed	20	20	20	20	40	40	50	70	70	100	100	150
If up titration needed*	20	20	20	40	40	50	70	70	100	100	150	150
If down titration needed*	#	#	20	20	20	40	40	50	70	70	100	100

* Up or down titrations are only applicable when the criteria for dose adjustment has been met;

Contact the medical monitor if down titration is needed

ESA Rescue Therapy

Protocol v2.0 allows subjects to receive ESA rescue treatment twice. If a third ESA treatment is required subject will be discontinued from the study treatment.

If, upon implementation of protocol v2.0, a subject has already received 3 or more ESA treatments (under protocol v1.0) they can initially continue in the study. The subject will, however, be discontinued from study treatment if a further ESA rescue treatment is required.

13 ATTACHMENT 1: NON-SUBSTANTIAL AMENDMENT 1

I. The purpose of this amendment is:

Non-Substantial Changes
1. Update contact details of key sponsor personnel
DESCRIPTION OF CHANGE:
Update the sponsor personnel to be contacted for SAE to the Product Safety & Pharmacovigilance group and the affiliation of the medical monitor and clinical research contact.
RATIONALE:
To provide the most up-to-date information for the key sponsor personnel.
2. Update abbreviation list
DESCRIPTION OF CHANGE:
Add ANOVA, DD-CKD, IUD, IUS, MRI, NDD-CKD, PPD, PPK/PD and SmPC to the abbreviation list. Delete ANCOVA, APEBV, APGD, BIW, CHOIR, CIOMS, CL/F, Composite Safety Endpoint, DSP, (e)CTD, EDTA, ELISA, EU, EWB, FDA, FWB, GGT, GMP, hCG, Hct, IB, IMPD, IND, INN, k _a , kg, Ki, LLN, LSO, MedDRA, mg, min, mL, MTD, NASH, NONMEM, PCS, PD, PHI, PK, pmp, QW, SOC, SQ, TESAE, t _{max} , V/F, VHL, WHODRL and Wk from the abbreviation list.
RATIONALE:
Complete abbreviation list.
3. Update post study follow-up
DESCRIPTION OF CHANGE:
Update wording to include follow-up of SAEs, cardiovascular and thromboembolic AEs during the post study follow-up and to remove the word 'hospitalizations'.
RATIONALE:
The additional wording is to provide clarification on events that are required for collection during the post study follow-up period. Information about hospitalizations is already stated in Section '5.3.3.2 Hospitalizations' and is therefore removed from the description of the post study follow-up.
4. Update planned study period
DESCRIPTION OF CHANGE:
Update the planned study period.

RATIONALE:
To reflect current recruitment and completion timelines of the study.
5. Clarify study population description

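### The Appendix 3 conversion table raises the weekly dose of a QW 50 mg subject who needs a dose reduction

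*Protocol*

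**What the plan says.** Section 12.3 covers subjects who entered under protocol v1.0, when maintenance dosing could be QW, twice weekly (BIW) or TIW, and who re-consent to v2.0, where all dosing is TIW. The order of steps is fixed: "At this visit it is first determined if the subject would need a dose titration according to the dose adjustment rules" of Section 5.1.2. The new TIW dose is then read from one of three tables, one per current frequency, each with a row for no titration, up titration and down titration. For once-weekly subjects: "Subjects in the maintenance period on QW dosing will change to TIW dosing immediately, per the conversion table below".

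In the 50 mg column of the QW table the three rows read 20, 20 and 20 mg TIW. In the down row of all three tables the lowest doses show `#` instead of a dose, with the footnote "Contact the medical monitor if down titration is needed". Section 5.1.2 lists 20 mg as the lowest dose step and says "Contact the Medical Monitor if dose adjustments would lead to doses outside the limits of the dose step range", naming doses below 20 mg as one such case.

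The appendix is printed a second time after Appendix 9, with the same values in the QW table ("Subjects in the maintenance period on QW dosing will change to TIW dosing immediately, per conversion table below"), so the cell is not a text-extraction slip.

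**The concern.** The step in which the site decides on titration has no effect for QW 50 mg, and the dose it leads to moves the wrong way. Under Table 3 of Section 5.1.2, a maintenance reduction is due at Hb 12.0 to <13.0 g/dL unless Hb has fallen by more than 1.0 g/dL over 4 weeks, or at Hb 10.5 to <12.0 g/dL with a rise above 1.0 g/dL. A QW 50 mg subject in either state is given more drug per week, with no prompt to call the medical monitor. At stake is the dosing of individual subjects with high or fast-rising Hb, and the consistency of a written dosing instruction. The trial's conclusions are not in question.

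**Working it through.** **Inputs.** The 12 columns and three rows of the TIW, BIW and QW tables in Section 12.3; the dose steps in Section 5.1.2 (20, 40, 50, 70, 100, 150, 200, 250, 300 mg). SAP Section 6.5.4 takes weekly dose as dose × 3 under TIW, and uses the recorded frequency for subjects randomized before v2.0.

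**Formula.** Current weekly mg = dose × 1 (QW), × 2 (BIW) or × 3 (TIW). New weekly mg = TIW dose × 3.

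**The cell itself.** Now: 50 × 1 = 50 mg/week. After: 20 × 3 = 60 mg/week. Change: 60/50 − 1 = +20%. To reduce 50 mg/week on a TIW schedule, each dose must be below 50/3 = 16.7 mg, which is under the lowest step.

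**The floor.** The lowest TIW regimen is 3 × 20 = 60 mg/week. Source doses at or just above it:

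| Current dose | mg/week now | Down cell | mg/week after | Change |
|---|---|---|---|---|
| QW 20 | 20 | `#` | – | – |
| QW 40 | 40 | `#` | – | – |
| BIW 20 | 40 | `#` | – | – |
| **QW 50** | **50** | **20 mg TIW** | **60** | **+20%** |
| TIW 20 | 60 | `#` | – | – |
| QW 70 | 70 | 20 mg TIW | 60 | −14.3% |
| BIW 40 | 80 | 20 mg TIW | 60 | −25% |

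Five source doses sit at or below 60 mg/week; QW 50 is the only one without `#`.

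**All down cells.** 36 columns less 4 `#` leaves 11 (TIW) + 11 (BIW) + 10 (QW) = 32 numeric cells. Thirty lower the weekly dose, by 10% to 50%. One leaves it unchanged (QW 120 to 40 mg TIW, 120 mg/week before and after). One raises it: QW 50.

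**Is weekly mg the right yardstick?** The weekly doses available on TIW are 60, 120, 150, 210, 300, 450, 600, 750 and 900 mg. Choosing the one nearest to the current weekly dose reproduces the no-titration row in 12/12 TIW, 12/12 BIW and 12/12 QW columns. Protocol Section 2.2.2 also describes the expected maintenance reduction in terms of total weekly dose.

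**The case against.** **Per intake, the dose falls.** SAP Section 6.5.4 defines a dose change as a change in mg per intake, and on that basis 50 to 20 mg is a 60% cut. One step down from 50 mg is 40 mg, within range, so the Medical Monitor rule of Section 5.1.2, read per intake, is not triggered. This is a fair reading of that section, but the table does not follow it. QW 40 would also fall per intake (40 to 20 mg, again within range), yet it carries `#`.

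**The cell follows a recipe.** Moving one column to the left in the QW table and then taking the no-titration dose reproduces all 10 numeric QW down cells; for QW 50 this runs through 40 mg QW to 20 mg TIW. That is probably how the value arose. The same recipe gives 20 mg TIW for QW 40, where the table prints `#`. The recipe was overridden there and not one column over.

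**Down equals no titration elsewhere.** This is true in 11 of the 32 numeric columns. In 9 of them the no-titration dose already lowers the weekly dose, and QW 120 is unchanged. The no-titration row also accepts larger rises (QW 20 +200%, QW 40 +50%), but those subjects have not met a reduction criterion.

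**Milligrams are not effect.** Protocol Section 2.2.2 says plasma EPO rose more than linearly with dose. If response scaled as dose to the power b (an assumption), three 20 mg doses would do less than one 50 mg dose once b exceeds ln 3/ln 2.5 = 1.20. This stands: the net effect on erythropoiesis cannot be told from the documents.

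**Reach and safeguards.** Only v1.0 subjects on QW 50 mg who met a reduction criterion at the re-consent visit are exposed. The QW arms were one third of the v1.0 allocation, and a third of those subjects were on placebo. If v1.0 started at today's 210 or 300 mg/week, 50 mg/week is a 76% or 83% cut (1 − 50/210; 1 − 50/300), against the 22% to 35% expected, so numbers are probably small. Dosing stops at Hb ≥13.0 g/dL, and "If Hb increases by > 2.0 g/dL within 4 weeks, the dose should be reduced by 1 dose step". HemoCue is read at treatment visits, investigators may depart from the rules for safety after discussion with the Medical Monitor, and at the next 4-weekly review a further reduction from 20 mg TIW would prompt contact. All of this stands, and it limits the harm. It does not make the cell right.

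**Conclusion.** The concern holds. As written, the QW 50 mg down-titration cell raises the weekly dose from 50 to 60 mg (+20%) and omits the medical monitor prompt given for every other source dose at or below 60 mg/week. The finding rests on weekly mg as the basis of the tables, which the no-titration rows and the `#` at QW 40 both support.

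The consequence is small. The documents give no count of subjects on QW 50 mg. EU responder status is normally settled before maintenance: entry needs Hb ≥11.0 g/dL with a rise of ≥1.0 g/dL at two consecutive visits, which also meets the Hb part of the response definition in either baseline stratum. Any effect on the US weeks 28–52 average is at most small. Protocol Section 7.4.1.2 already plans a sensitivity analysis of both primary endpoints in subjects randomized after v2.0, although SAP Table 14 does not list it for the US endpoint.

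Conversions may be over: the footnote in Section 12.3 uses the past tense ("Up or down titrations were only applicable when the criteria for dose adjustment has been met"), while the second copy uses the present ("Up or down titrations are only applicable when the criteria for dose adjustment has been met"). The point should be corrected because it is a definite error in a dosing instruction and costs almost nothing to put right.

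**What to change.** Replace the QW 50 mg down-titration entry with `#` in both copies of the table (Section 12.3, part c, and the repeat after Appendix 9). From the Dosing Decisions eCRF data described in SAP Section 6.5.4, list any v1.0 subject who was on QW 50 mg, met a reduction criterion at the re-consent visit and was moved to 20 mg TIW, and have the medical monitor review each case. If all conversions are complete, the listing is the only step with practical effect. The cost is one cell in two places and one listing from data already collected; no analysis changes.

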12.4 Appendix 4: Instructions for Subjects Requiring Dialysis

Subjects who initiate temporary or permanent dialysis treatment are allowed to continue in the study. All modes of dialysis, i.e., HD, hemodiafiltration (HDF) and peritoneal dialysis are allowed.

12.4.1 Dosing

- Subjects should continue with the same dose and dose frequency of study drug as they were on prior to dialysis initiation.
- For HD/HDF subjects it is recommended that study drug is administered any time after completion of dialysis (if dosing is scheduled on a dialysis day) to avoid potential bias on certain study assessments.

12.4.2 Dose Adjustment

- The dose adjustment rules remain unchanged (see Section 5.1.2).
- The maximum allowed dose in subjects on permanent dialysis is 3.0 mg/kg (based on dry weight in HD subjects and weight minus abdominal fluid based on last filling in peritoneal dialysis subjects) or 400 mg per administration, whichever is lower.

12.4.3 Rescue Therapy – ESA Use

If subjects meet the criteria for ESA rescue therapy whilst on dialysis, ESAs will be administered IV or SC according to the Package Insert or SmPC of the respective ESA for dialysis patients.

12.4.4 Health Related Quality of Life

Additional questionnaires will be completed on day of first dialysis, 4 weeks later and 12 weeks later, prior to initiation of the procedure.

12.4.5 Timing of Study Assessments

- If a study visit occurs on a dialysis day, all study assessments should be performed before start of dialysis.
- BP and HR should be measured in triplicate prior to and after end of dialysis (HD/HDF subjects only).

12.5 Appendix 5: Short Form-36 Health Survey (SF-36)

Your Health and Well-Being

This survey asks for your views about your health. This information will help keep track of how you feel and how well you are able to do your usual activities. *Thank you for completing this survey!*

For each of the following questions, please tick the one box that best describes your answer.

1. In general, would you say your health is:

Excellent	Very good	Good	Fair	Poor
▼	▼	▼	▼	▼
 1	 2	 3	 4	 5

2. Compared to one year ago, how would you rate your health in general now?

Much better now than one year ago	Somewhat better now than one year ago	About the same as one year ago	Somewhat worse now than one year ago	Much worse now than one year ago
▼	▼	▼	▼	▼
 1	 2	 3	 4	 5

3. The following questions are about activities you might do during a typical day. Does your health now limit you in these activities? If so, how much?

Yes, limited a lot	Yes, limited a little	No, not limited at all
▼	▼	▼

- a Vigorous activities, such as running, lifting heavy objects, participating in strenuous sports 1 2 3
- b Moderate activities, such as moving a table, pushing a vacuum cleaner, bowling, or playing golf..... 1 2 3
- c Lifting or carrying groceries 1 2 3
- d Climbing several flights of stairs 1 2 3
- e Climbing one flight of stairs 1 2 3
- f Bending, kneeling, or stooping 1 2 3
- g Walking more than a mile..... 1 2 3
- h Walking several hundred yards..... 1 2 3
- i Walking one hundred yards 1 2 3
- j Bathing or dressing yourself 1 2 3

4. During the past 4 weeks, how much of the time have you had any of the following problems with your work or other regular daily activities as a result of your physical health?

	All of the time	Most of the time	Some of the time	A little of the time	None of the time
	▼	▼	▼	▼	▼
a Cut down on the amount of time you spent on work or other activities.....	 1	 2	 3	 4	 5
b Accomplished less than you would like	 1	 2	 3	 4	 5
c Were limited in the kind of work or other activities	 1	 2	 3	 4	 5
d Had difficulty performing the work or other activities (for example, it took extra effort)	 1	 2	 3	 4	 5

5. During the past 4 weeks, how much of the time have you had any of the following problems with your work or other regular daily activities as a result of any emotional problems (such as feeling depressed or anxious)?

	All of the time	Most of the time	Some of the time	A little of the time	None of the time
	▼	▼	▼	▼	▼
a Cut down on the amount of time you spent on work or other activities.....	 1	 2	 3	 4	 5
b Accomplished less than you would like	 1	 2	 3	 4	 5
c Did work or other activities less carefully than usual	 1	 2	 3	 4	 5

6. During the past 4 weeks, to what extent has your physical health or emotional problems interfered with your normal social activities with family, friends, neighbours, or groups?

Not at all	Slightly	Moderately	Quite a bit	Extremely
▼	▼	▼	▼	▼
 1	 2	 3	 4	 5

7. How much bodily pain have you had during the past 4 weeks?

None	Very mild	Mild	Moderate	Severe	Very severe
▼	▼	▼	▼	▼	▼
 1	 2	 3	 4	 5	 6

8. During the past 4 weeks, how much did pain interfere with your normal work (including both work outside the home and housework)?

Not at all	A little bit	Moderately	Quite a bit	Extremely
▼	▼	▼	▼	▼
 1	 2	 3	 4	 5

9. These questions are about how you feel and how things have been with you during the past 4 weeks. For each question, please give the one answer that comes closest to the way you have been feeling. How much of the time during the past 4 weeks...

	All of the time	Most of the time	Some of the time	A little of the time	None of the time
a	▼	▼	▼	▼	▼
Did you feel full of life?	 1	 2	 3	 4	 5
b					
Have you been very nervous?	 1	 2	 3	 4	 5
c					
Have you felt so down in the dumps that nothing could cheer you up?	 1	 2	 3	 4	 5
d					
Have you felt calm and peaceful?	 1	 2	 3	 4	 5
e					
Did you have a lot of energy?	 1	 2	 3	 4	 5
f					
Have you felt downhearted and low?	 1	 2	 3	 4	 5
g					
Did you feel worn out?	 1	 2	 3	 4	 5
h					
Have you been happy?	 1	 2	 3	 4	 5
i					
Did you feel tired?	 1	 2	 3	 4	 5

10. During the past 4 weeks, how much of the time has your physical health or emotional problems interfered with your social activities (like visiting with friends, relatives, etc.)?

All of the time	Most of the time	Some of the time	A little of the time	None of the time
▼	▼	▼	▼	▼
 1	 2	 3	 4	 5

11. How TRUE or FALSE is each of the following statements for you?

Definitely true	Mostly true	Don't know	Mostly false	Definitely false
▼	▼	▼	▼	▼

- a I seem to get ill more easily than other people 1 2 3 4 5
- b I am as healthy as anybody I know 1 2 3 4 5
- c I expect my health to get worse 1 2 3 4 5
- d My health is excellent 1 2 3 4 5

Thank you for completing these questions!

